An update of the Phase 1 trial done at the Mayo clinic ([name], personal communication) was provided. Nineteen MMM patients were enrolled between June, 2008 and March, 2009. Most of the subjects were intermediate-2 or high risk by the International Prognostic Scoring System for MF. Median duration of disease at enrollment was 24 months (range, 1-173 months). Most were RBC-transfusiondependent and had symptomatic splenomegaly. Three subjects enrolled into the 2.5 mg/d, 3.0 g/d, and 3.5 mg/d cohorts (given for 3 weeks, with one week break). The dose limiting toxicity (DLT) was bone marrow suppression which occurred in 2 of 3 subjects in the 3.5 mg/d cohort. 3 additional subjects received 3.0 mg/d confirming this as the MTD. 7 additional subjects were enrolled at the MTD of 3.0 mg/d. Because no efficacy was seen at 3.0 mg/d (21 of 28 days) the dose was decreased to 0.5mg/d (given continuously daily for 4 weeks; no break in therapy) after three cycles in 8 subjects. 7 subjects responded using the International Working Group for Myelofibrosis Research and Treatment criteria

for Clinical Improvement (IWGMRT CI). All responders had an IWG-MRT CI for anemia (6 previously RBC transfusion-dependent). 2 of these anemia responders also had a decrease in splenomegaly. The eligibility criteria excluded the possibility of an IWG-MRT CI for thrombocytopenia. However all 5 subjects with pre-study platelets of 50-100x109/L had an increase in their platelet number, with 3 of these achieving normal platelet levels. Responses occurred after a median of 4 months (range, 2-9 months) and only after reduction to 0.5mg/d in 5 responders including the 2 subjects with decreased spleen size. These responses occurred after 1 and 2 cycles after dose reduction, respectively (1-3 months). Responses were durable; 5 responders continue on-study.

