2.2.2. Secondary Endpoints

- Duration of response
- Time to response
- Best overall response as determined by International Working Group Criteria over the first 12 cycles (336 days) of study treatment
- Cytogenetic response in subjects with a baseline abnormality
- Molecular response (JAK2^{V617F} mutation burden) in peripheral blood in mutation positive subjects
- Bone marrow fibrosis improvement
- Quality of Life (QoL) assessments [the four components (Physical, Social/Family, Emotional and Functional Well-Being) and total of the 27-item FACT-G, together with the 13-item fatigue subscale, the total of the Additional Concerns, and a Likert Pain Scale for splenic pain.

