3. INVESTIGATIONAL PLAN

3.1. Overall design

CC-4047 is a phase 2, prospective, open-label study to determine the efficacy and safety of CC-4047 at a 0.5 mg dose, in combination with prednisone, to study further in subjects with primary, post polycythemia vera, or post essential thrombocythemia myelofibrosis

Screening:

Potential subjects will enter screening and be evaluated for the inclusion and exclusion criteria for the Treatment Period of this study. The screening period will not last more than 28 days. The assessments and procedures that will be performed during screening are outlined in Appendix M: Schedule of Events. Screening assessments will include an informed consent, medical history, review of prior medications, complete physical exam, ECOG performance status assessment, complete blood count (CBC) with differential, serum chemistries, urinalysis, thyroid function tests, 12-lead ECG, bone marrow biopsy and aspirate to confirm diagnosis and for standard cytogenetics, JAK2 mutation (by quantitative polymerase chain reaction [PCR], and PCR or fluorescent in situ hybridization (FISH) for bcr/abl, spleen and/or liver (if spleen is absent) measurements, and QoL Assessments.

Females of reproductive potential¹ must adhere to the scheduled pregnancy testing as required in the POMALYST REMSTM program. All study participants must be registered into the mandatory POMALYST REMSTM program, and be willing and able to comply with the requirements of the POMALYST REMSTM program.

Before starting study drug:

Subjects must follow pregnancy testing requirements as outlined in the POMALYST REMS TM program.

Treatment Period:

Subjects meeting all inclusion and exclusion criteria will receive 0.5mg CC-4047. Prednisone will be given during first 3 cycles of therapy. It will be dosed orally at the dose of 30 mg/day during cycle 1, 15 mg/day during cycle 2, and 15 mg every other day during cycle 3, and then it will be discontinued. Prednisone will be used from commercially available supplies.

Subjects will remain on study treatment in the Treatment Period in the absence of disease progression or toxicity warranting discontinuation of therapy. Twenty-eight days is considered one cycle of therapy. Subjects may be taken off study at 6 months if there is no response, however, they should continue to be followed until disease progression or initiation of an alternate therapy.

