5.3 Statistical Methodology

5.3.1. Primary Endpoint

The primary endpoint of this trial is best overall response. An evaluable subject will be classified as a treatment success for the primary endpoint if the subject's best overall response is CR, PR or CI (Clinical Improvement) as determined by International Working Group Criteria over the first 6 cycles of study treatment at 0.5mg/day dose. The largest success proportion where the proposed treatment regimen would be considered unpromising in this population is 5%, representing the probability of a response by chance. The smallest success proportion that would warrant further subsequent studies with the proposed treatment regimen in this subject population is 20%.

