5.3.3. Analysis Plan

Primary Endpoint

The observed response rate over the first 6 cycles of therapy at 0.5mg/day will be estimated by the number of responses (confirmed CR, PR or CI) over the first 6 cycles divided by the total number of evaluable subjects. Confidence intervals for the true response rates will be calculated according to the approach of Duffy and Santner.

Secondary Endpoints

Duration of response: duration of response is defined as the date at which the subject's objective status is first noted to be a CR, PR or CI to the date progression is documented (if one has occurred) or to the date of last follow-up (for those subjects who have not progressed).

Time to response: The time to response is defined as the time from study registration to the first date at which the subject's objective status was classified as a response (CR, PR or CI). In subjects who do not achieve a response, time to response will be censored at the subject's last evaluation date. The distribution for each of these event-time variables (duration of response and time to response) will be estimated by Kaplan-Meier curves.

Best overall response as determined by the International Working Group Criteria over the first 12 cycles of study treatment: will be estimated by the number of responses (confirmed CR, PR or CI) over the first 12 cycles divided by the total number of evaluable subjects. Confidence intervals for the true response rates will be calculated according to the approach of Duffy and Santner.

Cytogenetic responses and molecular response: cytogenetic responses and molecular responses will be summarized as well as evaluated graphically. Correlations among clinical responses and laboratory variables will be explored using a Wilcoxon/Kruskal-Wallis test for ordered contingency tables. Mutation status will be explored in relation to clinical outcome (response) using Fisher's exact test.

Quality of Life (QOL) assessments: For each of the QOL assessment components, changes from baseline to each of the follow-up time points will be reported. The change will be compared between two subgroups: subjects who response to the treatment and subjects who do not response. Normality testing via the Shapiro-Wilk procedure will determine whether or not parametric or nonparametric procedures will from the basis for analysis (two-sample t-test, Wilcoxon rank sum test).

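### The responder versus non-responder quality-of-life comparison has no landmark, so it cannot be read as benefit from response

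*Combined protocol and SAP*

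**What the plan says.** All references are to the combined protocol and SAP.

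- **QoL analysis (5.3.3).** For each QoL component, "changes from baseline to each of the follow-up time points will be reported". The next sentence reads: "The change will be compared between two subgroups: subjects who response to the treatment and subjects who do not response". The test is a two-sample t-test or a Wilcoxon rank sum test: "Normality testing via the Shapiro-Wilk procedure will determine whether or not parametric or nonparametric procedures" are used. The paragraph gives no landmark, response date, repeated-measures model or rule for missing QoL.
- **Who is a responder.** The QoL paragraph does not define the term. Section 5.3.1 defines a treatment success as a subject whose "best overall response is CR, PR or CI (Clinical Improvement) as determined by International Working Group Criteria over the first 6 cycles". Section 2.2.2 adds a second window: "Best overall response as determined by International Working Group Criteria over the first 12 cycles (336 days) of study treatment".
- **Who stays.** Section 3.1: "Subjects may be taken off study at 6 months if there is no response". The same sentence goes on to require follow-up until progression or another therapy. Section 3.8 lists lack of therapeutic effect as a reason to stop study drug. Section 3.9 sets three-monthly follow-up after discontinuation.
- **When response comes.** Section 1.2 (addendum of 11/10/09) says of the phase 1 study of the same drug: "Responses occurred after a median of 4 months", with a range of 2 to 9 months.

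**The concern.** Best overall response is settled only when the 6- or 12-cycle window closes. Used as a grouping variable at earlier visits, it sorts subjects by something that has not yet happened. Three consequences follow if the contrast is read as the effect of response on QoL.

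1. At early visits the responder group includes people not yet in response, which dilutes any real benefit.
2. A subject must stay long enough to respond, so those who leave early fall into the non-responder group. If they feel worse before leaving, responders look better before anyone has responded.
3. After month 6 the non-responders still observed may be a selected few, because lack of response is itself a ground for leaving.

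What is at stake is the interpretation of a listed secondary endpoint for which formal tests are planned. No go/no-go decision depends on it.

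**Working it through.** **1. The plan's own figures.** The documents give no figure for the QoL comparison. The two-stage design (stop if 1 or fewer of 20 succeed; promising if 4 or more of 37) reproduces exactly. With X1 ~ Bin(20, p) and X2 ~ Bin(17, p), summing P(X1 = x)·P(X2 ≥ 4 − x) over x = 2 to 20 gives 0.0898 at p = 0.05 and 0.9100 at p = 0.20, against the stated 0.09 and 0.91. QoL does not enter this calculation.

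**2. Timing of response.** Section 1.2 cites a median of 12 weeks for lenalidomide plus prednisone (84/28 = 3 cycles) and 4 months for pomalidomide (about 122/28 = 4.3 cycles). The upper end of the pomalidomide range, 9 months, is about 274/28 = 9.8 cycles. A subject can therefore be a non-responder over 6 cycles and a responder over 12, so the unstated window matters.

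**3. Dilution at early visits.** Let f be the fraction of eventual responders who have responded by a visit, and D the true gain from being in response. If the groups are otherwise alike and missingness is unrelated to QoL, the expected contrast is f × D. Taking D = 0.50 SD as an assumption:

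| f | Expected contrast (SD) |
|---|---|
| 0.25 | 0.125 |
| 0.50 | 0.25 |
| 0.75 | 0.375 |
| 1.00 | 0.50 |

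A simulation with an assumed response-time pattern (f = 0.00, 0.27, 0.59, 0.82, 1.00 at months 1, 3, 6, 9, 12) agrees: 0.00, 0.14, 0.30, 0.42, 0.50.

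**4. Early leavers.** The randomized phase 2 study in section 1.2 had arms of 22, 19, 22 and 21, response rates of 23%, 16%, 36% and 19%, and 20 responders (5 + 3 + 8 + 4). Among the 62 subjects with at least 3 cycles the rates were 38%, 23%, 40% and 25%. These fit 5/13, 3/13, 8/20 and 4/16, which total 20/62. On this reconstruction no responder came from the 84 − 62 = 22 who left early.

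- All arms: early leavers are 22 of 84 − 20 = 64 non-responders, or 34%.
- The 0.5 mg plus prednisone arm, closest to this trial: 2 of 22 − 8 = 14, or 14%.

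If early leavers score lower by δ while still observed, the spurious contrast is that share times δ. For δ = 0, 0.5 and 1 SD (assumed) it is 0, 0.07 to 0.17, and 0.14 to 0.34 SD.

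**5. Both mechanisms together.** The simulations below give responders minus non-responders in SD units. Response, dropout and QoL correlation are all assumed. Informative dropout means that poor QoL makes leaving more likely and that about 70% of non-responders leave at month 6.

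| Scenario | Month 1 | 3 | 6 | 9 | 12 |
|---|---|---|---|---|---|
| No effect, dropout unrelated to QoL | about 0 | about 0 | about 0 | about 0 | about 0 |
| No effect, informative dropout | +0.24 | +0.15 | +0.11 | −0.27 | −0.33 |
| True 0.50, informative dropout | 0.24 | 0.34 | 0.52 | 0.19 | 0.18 |

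In the second row about 15 to 17% of non-responders are still observed at months 9 and 12.

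**6. Effect of the remedy.** Classifying subjects still observed by their status at the visit, with a true effect of 0.50, gives 0.51 and 0.50 at months 3 and 6 without informative dropout, and 0.48 and 0.44 with it. The timing problem is repaired; some dropout bias remains.

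**7. Precision.** At a 20% response rate, 37 × 0.20 = 7.4, so about 7 against 30. A two-sided 5% t-test (an assumed level, as the plan gives none for QoL) has power 0.21 for 0.5 SD and needs 1.21 SD for 80%.

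**The case against.** **The plan claims no causal effect.** The secondary objective in section 2.1.2 is only to explore the nature and quality of responses. A plain description of how the two groups differ is legitimate. This stands: the bias exists only relative to a reading of the contrast as benefit from response. But formal tests are planned, and nothing labels them descriptive or warns against that reading.

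**Testing at every visit and grouping by eventual response are inferences.** The text says changes to each time point are reported and the change is compared. This stands as a caveat, although best overall response is the only subject-level definition given.

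**The QoL schedule is not visible.** It is in Appendix M, which was not in the text available; that is not counted against the plan. How many early QoL visits exist is therefore unknown.

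**The response times do not transfer directly.** One is for lenalidomide. The other rests on 7 responders in a study that started at 2.5 to 3.5 mg/d, 5 of whom responded only after reduction to 0.5 mg/d. With a 6-cycle window, those counted as responders would also have an earlier median. A reader might infer that at least half of the responders here will not have responded through cycles 2 to 4; the documents do not support that for this regimen.

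**Follow-up continues after non-responders leave.** A reader might infer that all of the roughly 30 non-responders could be missing by design after month 6. Sections 3.1 and 3.9 do not support this: removal is optional and follow-up is required. What remains open is whether QoL is collected in that follow-up.

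**Conclusion.** The point holds as a limit on interpretation. Without a landmark or time-varying status, the planned comparison cannot separate benefit from response from the timing of response and from who stays under observation. A reader might go further and call the comparison biased outright. The documents do not support that: if response has no effect on QoL and dropout is unrelated to QoL, the expected contrast is about zero at every visit. Otherwise its size and direction cannot be determined from the documents, and early and late distortions can have opposite signs. The SD figures above are illustrations on assumed inputs.

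The conclusion assumes that responder means best overall response over 6 or 12 cycles and that the tests are applied at several visits. The 20/37 decision rule, its 0.09 significance level and its 91% power are untouched. This is a worthwhile, low-cost improvement to a secondary analysis.

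**What to change.** Amend the QoL paragraph of section 5.3.3 as follows:

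- State which response window defines a responder for QoL.
- Make the formal comparison a landmark at the end of cycle 6: classify subjects still under observation by response up to that date, and compare change from baseline at that visit. Section 3.1 already brings subjects with local visits back to the study centre then.
- Report numbers observed and missing in each group.
- Show all other visits descriptively.
- State how missing QoL is handled, and whether QoL is collected after treatment stops. The landmark alone does not remove informative dropout.
- Say that the contrast is an association and not evidence that response improves QoL.

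The cost is SAP wording and slightly different programming; no new data collection is evident from the text available. The downsides are fewer formal tests, exclusion of subjects lost before the landmark, and counting subjects who first respond in cycles 7 to 12 as non-responders in this comparison. If the 6-cycle window was always intended, the cycle 6 result will be close to one already planned.

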In addition, results of randomized Phase II study have been published (Tefferi, 2009). In a phase II randomized, multicenter, double-blind, adaptive design study, four treatment arms were evaluated: pomalidomide (2 mg/day) + placebo, pomalidomide (2 mg/day) + prednisone, pomalidomide (0.5 mg/day) + prednisone, and prednisone + placebo. Pomalidomide was administered for up to twelve 28-day treatment cycles. Prednisone (30 mg/day) was given in a tapering dose schedule during the first three cycles. Response was assessed by International Working Group criteria. Eighty four patients with MMMassociated anemia were randomly assigned to the above-listed treatment arms: 22, 19, 22 and 21, respectively. All active patients have completed six cycles of treatment. Response in anemia was documented in 20 patients, including 15 who became transfusionindependent. Response rates in the four treatment arms were 23%, 16%, 36% and 19%. The corresponding figures for patients receiving ≥ 3 cycles of treatment (n=62) were 38%, 23%, 40% and 25%. Response to pomalidomide ± prednisone was durable (range 3.2-16.9+ months) and significantly better in the absence of leukocytosis (37% vs. 8%; p=0.01); JAK2V617F or cytogenetic status did not affect response. Grade ≥ 3 toxicities were infrequent and included (in each treatment arm) neutropenia (9%-16%-5%-5%), thrombocytopenia (14%-16%-9%-5%) and thrombosis (9%-5%-0%-0%). Pomalidomide therapy at $0.5 \pm an$ abbreviated course of prednisone is well tolerated in patients with myelofibrosis and active in the treatment of anemia.

Finally, 20 patients have been accrued into current study so far, with starting dose of 3mg/day. After median follow up of 2 months, most patients had to interrupt the therapy due to side effects: 13 patients experienced myelosuppression, 3 had rash/swelling. The study accrual has been put on hold, pending modification of the dose to 0.5mg/day (given continuously).

ADDENDUM 3/30/11:

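### The responder versus non-responder comparison of quality-of-life change does not use the baseline score as a covariate; a baseline-adjusted estimate should stand beside it, labelled exploratory

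*Combined protocol and SAP*

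**What the plan says.** QoL is a secondary endpoint in section 2.2.2, with several scores: "Quality of Life (QoL) assessments [the four components (Physical, Social/Family, Emotional and Functional Well-Being) and total of the 27-item FACT-G", together with a fatigue subscale, an Additional Concerns total and a Likert scale for splenic pain. Section 3.1 places the first measurement at screening: "spleen and/or liver (if spleen is absent) measurements, and QoL Assessments".

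Section 5.3.3 sets out two analyses. The first is descriptive: "For each of the QOL assessment components, changes from baseline to each of the follow-up time points will be reported". The second is the comparison at issue: "The change will be compared between two subgroups: subjects who response to the treatment and subjects who do not response". The test is picked by a normality check: "Normality testing via the Shapiro-Wilk procedure will determine whether or not parametric or nonparametric procedures will from the basis for analysis", the two candidates being "two-sample t-test, Wilcoxon rank sum test".

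Neither test takes a covariate. No ANCOVA or mixed model for QoL appears anywhere in the documents. The QoL paragraph asks for no estimate of the group difference and no confidence interval. It gives no SD, effect size, alpha or power, and does not say whether the 6-cycle or the 12-cycle response defines the groups.

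**The concern.** Both tests act on the raw change score. Subtracting baseline fixes its coefficient at 1, whereas ANCOVA estimates that coefficient from the data. When the correlation between baseline and follow-up is below 1, the fixed coefficient adds noise. That matters when one of the two groups may hold only a handful of subjects.

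There is also a possible bias. Responder status is an outcome, not a randomised assignment, so the groups may start at different QoL levels. If scores also regress to the mean, the group that starts higher will tend to gain less for reasons unrelated to response.

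At stake is how a reader interprets the link between response and QoL. That link is part of a secondary analysis. It does not touch the primary endpoint or either stage of the decision rule.

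**Working it through.** **The plan's own figures.** The documents give none for the QoL comparison. The two-stage rule, used here only for group sizes, reproduces: with 20 then 17 subjects, stopping at 1 or fewer successes and requiring 4 or more of 37, the exact binomial gives alpha 0.0898 (stated 0.09) and power 0.9100 (stated 0.91).

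**Inputs from the documents.** There are 37 evaluable subjects (5.3.2). The number of responders is set at three levels:
- 4, the smallest count that declares promise (5.3.2).
- 7, from 0.20 × 37 = 7.4 (target rate, 5.3.1).
- 13, from 0.36 × 37 = 13.3 (anemia response rate for the combination in the earlier randomised study, section 1.2).

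**Assumptions, not in the documents.** Equal SD at both times; baseline/follow-up correlation r of 0.3 to 0.7; two-sided 0.05; normal scores.

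**Step 1: precision with similar baselines.**
- Variance of change: 2(1 − r)SD².
- Residual variance after adjustment: (1 − r²)SD².
- Ratio: (1 − r²) / [2(1 − r)] = (1 + r)/2.
- At r = 0.3, 0.5, 0.7 this is 0.65, 0.75, 0.85.

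Power from the noncentral t, change score → adjusted:

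| Responders v non-responders | True difference | r = 0.3 | r = 0.5 | r = 0.7 |
|---|---|---|---|---|
| 4 v 33 | 0.5 SD | 0.12 → 0.16 | 0.15 → 0.19 | 0.22 → 0.25 |
| 7 v 30 | 0.5 SD | 0.17 → 0.23 | 0.21 → 0.27 | 0.32 → 0.37 |
| 13 v 24 | 0.5 SD | 0.22 → 0.32 | 0.29 → 0.37 | 0.45 → 0.51 |
| 7 v 30 | 1 SD | 0.50 → 0.68 | 0.64 → 0.76 | 0.85 → 0.90 |

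**Step 2: precision when baselines differ.** If the groups differ by d SD at baseline, the ratio is multiplied by 1 + p(1 − p)d², where p = 7/37 = 0.189 and p(1 − p) = 0.153.
- d = 0.5: multiplier 1.038, so 0.75 becomes 0.78 and 0.85 becomes 0.88.
- d = 1: multiplier 1.153, so 0.75 becomes 0.87 and 0.85 becomes 0.98.

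**Step 3: bias under two models**, 7 v 30, r = 0.5, no effect of response, 4,000 simulated trials per setting.

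*Model A:* follow-up depends on baseline in the same way in both groups. The change score is off by (r − 1)d, which is (0.5 − 1) × 0.5 = −0.25 SD at d = 0.5.

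*Model B:* the groups differ stably and change in parallel.

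| Model | d | Change score: mean error, rejection | Adjusted: mean error, rejection |
|---|---|---|---|
| A | 0.5 | −0.25 SD, 9% | 0.01 SD, 6% |
| A | 1 | −0.50 SD, 21% | 0.00 SD, 5% |
| B | 0.5 | 0.01 SD, 6% | +0.26 SD, 10.5% |
| B | 1 | −0.01 SD, 5% | +0.50 SD, 23% |

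With d = 0, neither method is biased under either model. The documents do not say which model is closer to the truth, or what d is.

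**The case against.** The strongest objection is that adjustment is not clearly better here. The groups are not randomised, so this is the setting of Lord's paradox: under Model B the planned analysis is right and ANCOVA creates the bias. That stands. It rules out replacing the change score, but not reporting an adjusted estimate beside it.

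A reader might infer that the planned comparison is biased because responders differ before treatment. Section 1.2 does report anemia response as "significantly better in the absence of leukocytosis (37% vs. 8%; p=0.01", and the thalidomide-prednisone study found fewer circulating blasts and CD34+ cells in responders. Both results come from other studies, neither concerns QoL, and this document reports no baseline QoL by response. They make a baseline difference conceivable without establishing one.

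A reader might also infer that the baseline score goes unused. It does not: it is subtracted from every follow-up score. What is missing is its use as a covariate.

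Two further objections also stand:
- For a 0.5 SD difference, power stays at or below about 0.5 with either method, so adjustment does not make this an adequate test.
- Larger weaknesses remain. Early QoL time points may precede the response that defines the group, responders must stay on study long enough to respond, and no handling of missing QoL data is described. Baseline adjustment cures none of these.

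**Conclusion.** The point holds as a modest loss of precision, with bias possible in either direction. Under equal SDs and similar baselines, the planned comparison carries 1/0.85 = 1.18 to 1/0.75 = 1.33 times the adjusted variance at r of 0.7 to 0.5. At a 1 SD baseline gap and r = 0.7 the gain almost vanishes. The correlations and gaps are assumptions.

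The documents do not support saying that the planned comparison is biased, or that ANCOVA would be free of bias. They do support saying that the plan, as written, would not show whether the result depends on starting level. Severity is low: QoL is secondary, no hypothesis, alpha or decision rule attaches to this comparison, and the descriptive report of change is unaffected.

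**What to change.** In the QoL paragraph of section 5.3.3:
- Report baseline QoL by response group for each component.
- Keep the planned change-from-baseline comparison.
- Add, for each component and time point, the difference from an ANCOVA of follow-up score on baseline score and response group, with its 95% confidence interval; use a rank-based version where scores are clearly skewed.
- Label the comparison an exploratory association, because the groups are formed by response observed after baseline.
- State that where the two estimates disagree, both are shown along with the baseline difference, and neither is taken as the effect of response.

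The cost is a few lines of SAP text, simple programming and one degree of freedom, with no new data. The downside is two estimates that may disagree when baselines differ. With as few as 4 to 7 responders, the common-slope assumption can barely be checked.

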2.2. Endpoints

2.2.1. Primary Endpoint

- Best overall response as determined by International Working Group Criteria over the first 6 cycles (168 days) of study treatment
- Safety (type, frequency, severity [National Cancer Institute (NCI) Common Terminology Criteria for Adverse Events (CTCAE) version 3.0] of adverse events (AEs), and relationship of AEs to CC-4047)

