Toxicity: As per NCI CTCAE Version 3.0, the term toxicity is defined as adverse events that are classified as either possibly, probably, or definitely related to study treatment. Such adverse events will be captured by Principal Investigator and his staff in a database. The maximum grade for each type of toxicity will be recorded for each subject, including start/stop dates, and frequency tables for each group will be reviewed to determine toxicity patterns. In addition, we will review all adverse event data that is graded as 3, 4, or 5 and classified as either "unrelated or unlikely to be related" to study treatment in the event of an actual relationship developing.

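### The primary safety endpoint covers all adverse events, but the only safety tables specified are limited to events judged related to treatment

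*Combined protocol and SAP*

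**What the plan says.** Section 2.1.1 lists the safety of CC-4047 and prednisone among the primary objectives. Section 2.2.1 lists safety under the primary endpoint, as the type, frequency and CTCAE severity "of adverse events (AEs), and relationship of AEs to CC-4047". Nothing there limits the endpoint to related events; relationship is one of the things to be described.

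In section 5.3.3 the analysis headed Primary Endpoint deals with response only. Safety appears in the Toxicity paragraph at the end of that section, in four steps:

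- Definition: "the term toxicity is defined as adverse events that are classified as either possibly, probably, or definitely related to study treatment".
- Recording: "Such adverse events will be captured by Principal Investigator and his staff in a database".
- Tabulation: "The maximum grade for each type of toxicity will be recorded for each subject", and "frequency tables for each group will be reviewed to determine toxicity patterns".
- Remaining events: "we will review all adverse event data that is graded as 3, 4, or 5 and classified as either" unrelated or unlikely to be related, in case a relationship later emerges. No table or summary of these is specified.

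Section 5.4 bases the safety analyses on everyone who took any study drug. It also gives a stopping rule with its own definition, limited to events at least possibly related. Section 3.1 describes a "phase 2, prospective, open-label study to determine the efficacy and safety of CC-4047 at a 0.5 mg dose", and section 5.3.2 describes two cohorts (CC-4047 alone, then CC-4047 with prednisone), neither with a control.

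**The concern.** An endpoint that includes every adverse event needs a summary that includes every adverse event. Here the tables are built after an attribution filter, so the planned output does not deliver the stated endpoint. The relationship component suffers most: the split between related and unrelated cannot be shown if one side of it is left out of the tables.

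Attribution is hard in this setting. The person judging knows the treatment, and there is no control group to show the background rate. The disease also produces the same findings. Section 1.1.3 gives anemia in 50% to 70% of subjects at diagnosis and thrombocytopenia in 37% at presentation, while section 1.2 (2011 addendum) reports myelosuppression as dose-limiting for CC-4047. A low count during treatment can reasonably be put down to either.

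At stake is the reading of the primary safety result. Two investigators with identical patients could produce different tables, and a reader could not tell how many events lay outside them.

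**Working it through.** The plan gives no figure for the safety tables, so the check is mainly a comparison of text.

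**1. Event classes against the planned output.**

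| Event class | In endpoint (2.2.1) | Planned output (5.3.3) |
|---|---|---|
| Judged at least possibly related, any grade | Yes | Maximum-grade and frequency tables |
| Judged unrelated or unlikely, Grade 3 to 5 | Yes | Review, no table specified |
| Judged unrelated or unlikely, Grade 1 to 2 | Yes | None |

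**2. Other sections that might fill the gap.** Section 5.4 settles which subjects are included, not which events are shown. Section 4.1 sends serious events to the IND Office whatever their attribution, but that is expedited reporting, and non-serious events fall outside it. Neither supplies a table.

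**3. Direction.** For one event type, let A be a subject's maximum grade over all events and R the maximum over related events only (0 if none). The related events are a subset, so R ≤ A for every subject. Hence, for every grade g, the number of subjects with R ≥ g is at most the number with A ≥ g. Equality holds only if no subject's classification depends on an event judged unrelated. The bound applies to counts at or above a grade. A single cell for an exact maximum grade can move either way: a subject with a related Grade 2 and an unrelated Grade 3 event of the same type sits under Grade 2 in one table and Grade 3 in the other.

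**4. Size.** Let q be the all-event rate at or above a grade, and s the share of those subjects with a related event at or above that grade. Then tabulated rate = q × s. The documents give neither q nor s. Purely as an assumed range, with q = 20%:

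- s = 100%: 0.20 × 1.00 = 20%
- s = 75%: 0.20 × 0.75 = 15%
- s = 50%: 0.20 × 0.50 = 10%
- s = 25%: 0.20 × 0.25 = 5%

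This shows how the rate depends on s and is not an estimate. The documents do show how much a single call can weigh. Section 1.2 (2011 addendum) characterises the safety of single-agent 0.5 mg/day in 20 evaluable patients by one neutropenic fever and one leg DVT, both in the same patient. With 20 subjects, one call on one event moves that event's rate by 1/20 = 5 percentage points.

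**5. Efficacy design.** With X1 successes among the first 20 and X2 among the next 17, stopping at stage I is P(X1 ≤ 1), and declaring activity is P(X1 ≥ 2 and X1 + X2 ≥ 4). At true rates of 0.05 and 0.20 these give 0.7358 and 0.0692 for stopping, and 0.0898 and 0.9100 for declaring activity. Section 5.6 states 0.74, 0.07, 0.09 and 0.91, so its figures reproduce. No adverse-event count enters them.

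**The case against.** The strongest reply is that the plan does not ignore unrelated events. Severe ones are reviewed, serious ones are reported whatever the attribution, the related category is wide because it takes in merely possible relationship, and the documents already link myelosuppression and thrombosis to the drug, so such events may often be counted. There is no safety hypothesis to test, and section 5.1 calls safety a secondary objective. A related-event rate is also a legitimate quantity, misleading only if read as all-cause.

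Much of this stands and limits the consequence. It does not close the gap: a review without a specified table is not a summary of the endpoint, and low-grade events judged unrelated have no analysis at all. Section 5.1 conflicts with sections 2.1.1 and 2.2.1 on the rank of safety, but it supplies no all-event analysis either.

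Four stronger readings are tempting, and the documents do not support them:

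- *Only related events are recorded.* The word opening "Such adverse events will be captured by Principal Investigator and his staff in a database" points that way, but reviewing unrelated Grade 3 to 5 events requires that they be recorded and classified. Appendix M, the assessment schedule, was not available here, so collection of low-grade events cannot be ruled out.
- *An event blamed on prednisone alone is in or out depending on the section.* It is in under 2.2.1, which covers all events. It is also in under 5.3.3 on the natural reading, since section 3.5.1 names both drugs under treatment. What differs is the descriptor: 2.2.1 asks for "relationship of AEs to CC-4047", while 5.3.3 refers to study treatment.
- *A specific number of events would be missed among 37 subjects.* That is the efficacy target, and safety covers everyone dosed. Any such count would rest wholly on assumed rates.
- *The rates are not comparable with the cited studies.* The documents do not say whether those studies' rates are all-cause.

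**Conclusion.** The point holds as a mismatch between a stated endpoint and a stated analysis. The endpoint is all adverse events with their relationship; the only tables specified are conditional on relationship. Followed as written, the counts at or above any grade can match the all-event counts or fall below them, and unblinded attribution decides which. The direction follows from the definitions and needs no assumption. The size of the shortfall cannot be derived from the documents and could be zero. The gap is partial for Grade 3 to 5 events judged unrelated or unlikely, and complete for Grade 1 to 2 events so judged. The point should be corrected because it concerns a primary endpoint and the repair is cheap. It gives no ground for doubting the efficacy decision rules or the toxicity stopping rule, which carries its own definition in section 5.4.

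**What to change.** In section 5.3.3, specify a table of maximum grade per subject by event type for all adverse events whatever their attribution, by cohort, with everyone who took any study drug as the denominator. Show the related subset alongside and keep the word toxicity for that subset. At minimum, do this for Grade 3 to 5, which the plan already reviews.

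Use one attribution target in sections 2.2.1 and 5.3.3: relationship to study treatment, recorded as CC-4047, prednisone or both.

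The cost is one additional table and possibly some extra entry of low-grade events judged unrelated. The sample size, the interim and final efficacy rules and the stopping rule stay as they are.
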